### Medical history groupings:

‘Medical history of HIV’ will be defined as the occurrence of at least one of the medical history preferred terms ‘HIV infection’, ‘HIV disease’, and ‘HIV test positive’.

‘Medical history of hepatitis C’ is given if at least one of the preferred terms ‘Hepatitis C’, ‘Chronic hepatitis C’, ‘Hepatitis C virus test positive’, ‘Hepatitis C antibody positive’, ‘Hepatitis C infection’, ‘Hepatitis C chronic’ is reported in the medical history data.

‘Medical history of arthropathy’ will be defined as the occurrence of at least one of the medical history preferred terms ‘Arthropathy’ and ‘Haemophilic arthropathy’.

### Compliance:

Compliance of each patient will be calculated as:

Compliance (%) based on prophylaxis infusion count =  $100 * \frac{\text{number of actual prophylaxis infusions}}{\text{number of expected prophylaxis infusion}}$

Compliance (%) based on total infusion count =  $100 * \frac{\text{number of actual infusions}}{\text{number of expected prophylaxis infusion}}$

Number of expected prophylaxis infusions: Number of prescribed infusions per week / 7 \* period of prescribed frequency (days)

### Treatment administration:

Documented infusions with other FVIII products or with a dose of 0 IU will be excluded. Infusions with a missing dose will be counted for number of infusions and exposure days but will be excluded from other treatment administration analyses.

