### **6.4 Study Intervention Compliance**

Participant compliance with study intervention will be assessed at each visit.

Used and unused vials of study medication will be returned to the clinic at every site visit for accounting. Any discrepancies between actual and expected amount of returned vials must be discussed with the participant at the time of the visit, and any explanation must be documented in the source records.

The electronic patient diary (EPD) will be used to assess the participant's compliance with the treatment schedule/dose, and to reconcile study medication inventory. The EPD will be used to record date and time of self-administration of study intervention for prophylaxis as well as every bleeding episode with details of the bleeding and administered intervention. Data on the EPD will be transmitted on a regular basis.

The EPD will be reviewed at visits and at regular contacts with the participant during the study.

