## 8.1 Efficacy Assessments

This is a post authorization safety study (PASS). The efficacy endpoints are secondary endpoints for the study and include:

Secondary Endpoints throughout the study

- ABR

Other exploratory endpoints pre-specified throughout the study

- Percentage of participant with 0 spontaneous bleeds during a 6-month treatment
- Total number of exposures
- Consumption: dose/kg per participant/year
- Type, location and severity of bleeds, reason for each injection, and response to treatment of bleeds

Further endpoints are specified in the SAP.

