#### Each injection of Jivi:

- a. Date and time
- b. Injection record
- c. Individual vial number (bar code scan from vial label or manual entry) and units administered
- d. Reason for treatment

Prophylaxis

Spontaneous bleed first treatment

Trauma bleed first treatment

Follow-up treatment

Other

Injections of Jivi as part of protocol mandated visits and procedures will be recorded on the respective CRF pages.

All bleeding episodes (regardless if treated or not, or treated at home or under medical supervision) as well as any potential treatment with other hemophilia drugs will be recorded in the EPD:

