#### **General rules**

When appropriate, the following imputation rules will be implemented so as not to exclude participants from statistical analyses due to missing or incomplete data:

- **Missing time of infusions**

If an in-hospital infusion has a missing time, the time of the pre-infusion FVIII level measurement plus 1 minute will be used. If this time is also missing, 10:00 will be substituted.

- **Missing or incomplete adverse event (AE) start date**

If first study treatment falls within imputation range, incomplete start date is imputed as first day of treatment. Otherwise, it is imputed to the earliest date of the imputation interval.

Empty start date is not imputed. Incomplete stop date is always imputed as the latest date of the imputation interval. Empty stop date is not imputed and presumed to be ongoing.

- Missing or incomplete concomitant medication start and end date**

If first study treatment falls within imputation range, incomplete start date is imputed as first day of treatment. Otherwise, it is imputed to the earliest date of the imputation interval.

Empty start date is not imputed. Incomplete stop date is always imputed as the latest date of the imputation interval. Empty stop date is not imputed and presumed to be ongoing.

Partially missing dates of medications categorized as 'PRIOR FVIII THERAPY' will not be imputed. All these medications will be considered prior medications.

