### ABR:

$$\text{Annualized number of bleeds} = \frac{\# \text{ of bleeds} * 365.25 * 24 * 60}{\text{period}}$$

*Period* is defined as the number of minutes calculated from the date and time of the beginning of the evaluation period and the date and time of the end of the evaluation period.

Evaluation periods for study 19764:

- Main efficacy period: Time from injection at visit 3 to end of treatment
- Complete study: Time from first injection at visit 2 to end of treatment

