### **Other efficacy endpoints**

Unless otherwise mentioned, results will be presented for complete study periods.

- Percentages of participants with 0 bleeds, 0 joint bleeds, 0 spontaneous bleeds, during the following treatment periods:
  - Last 6 months
  - Last year

- Treatment administration (overall, prophylaxis, treatment of bleeds): number of infusions (all and per year), consumption (IU, IU/kg, IU/kg/year, IU/kg/infusion, IU/year, IU/infusion)
- Reason for infusion
- Bleeding attributes: type, location, intensity, number of infusions to control, response to treatment
- FVIII levels pre- and post-infusion and incremental recovery: Results will be displayed by visit and overall (means per participant across visits)
- Pre- and post-infusion FVIII levels which are invalid for the calculation of recovery will be listed
- Bleeds into pre-existing target joints (annualized number, proportion of participants with 0 such bleeds) for the complete study period as well as the main efficacy period (starting with Visit 3)
- All untreated bleeds of study 19764 will be listed.
- Dosing regimens at baseline, Visit 3, and end of study will be compared in shift tables
- All dosing frequencies, planned doses, and reasons for dose modifications will be listed

[figure not shown]

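### Infusions with a missing dose appear to add nothing to total and annualised factor consumption while follow-up time is unchanged, so this exploratory endpoint would be understated

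*SAP*

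**What the plan says.** The rule is in SAP 4.5 under Treatment administration: "Infusions with a missing dose will be counted for number of infusions and exposure days but will be excluded from other treatment administration analyses". Entries of 0 IU and infusions of other FVIII products have their own rule there and are not at issue.

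SAP 6.2 (Other efficacy endpoints) lists, under treatment administration, the number of infusions and "consumption (IU, IU/kg, IU/kg/year, IU/kg/infusion, IU/year, IU/infusion"), overall and separately for prophylaxis and treatment of bleeds. On the period covered it says: "Unless otherwise mentioned, results will be presented for complete study periods". The only definition of that period is among the evaluation periods under the ABR heading in SAP 4.5: "Complete study: Time from first injection at visit 2 to end of treatment".

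Protocol 8.1 names the endpoint among the other exploratory endpoints: "Consumption: dose/kg per participant/year".

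The imputation rules in SAP 4.3 cover infusion times (for example "If an in-hospital infusion has a missing time, the time of the pre-infusion FVIII level measurement plus 1 minute will be used"), adverse event dates and concomitant medication dates. They contain nothing for a missing dose. The same section promises counts of missing inhibitor and antibody measurements, but not of missing doses. The sensitivity analyses in SAP 6.2 do not address dose, as far as the unredacted text shows.

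**The concern.** The rule accepts that the infusion took place, since it counts as an infusion and as an exposure day, but gives it no units. For a mean per infusion this is ordinary complete-case handling. For a total, or a total divided by time, leaving the units out has the same effect as recording a dose of zero.

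The resulting error has one direction: reported consumption can only be too low. It is largest in participants who record poorly. Because no count of missing doses is planned, a reader of the report could not judge its size. At stake is the accuracy of one pre-specified exploratory endpoint.

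**Working it through.** The documents state no consumption figure and no missing-dose rate, so there is no planned figure to reproduce. The missing share and the dose ratio below are assumptions shown over a range.

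**Inputs**
- Regimen for illustration: 45 IU/kg every 5 days, the recommended start in SAP 3, with full adherence and prophylaxis only.
- Year length: 365.25 days, as in the ABR formula of SAP 4.5.
- m = share of infusions with a missing dose (assumed 1% to 20%).
- r = mean missing dose divided by mean recorded dose (assumed 0.5 to 1.5).

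**Formulas.** For N infusions over T years with mean recorded dose d per kg:
- actual consumption = N × d × [(1 − m) + m × r] / T
- reported under the rule, full period in the denominator = N × d × (1 − m) / T
- relative bias = −m × r / [(1 − m) + m × r], which reduces to −m when r = 1

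**Equal means (r = 1).** Actual: 45 × 365.25 / 5 = 3287 IU/kg/year.

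| m | Reported IU/kg/year | Bias |
|---|---|---|
| 1% | 3254 | −1% |
| 2% | 3222 | −2% |
| 5% | 3123 | −5% |
| 10% | 2959 | −10% |
| 20% | 2630 | −20% |

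The percentages are the same for every regimen, because the dose and interval cancel.

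**Unequal means.**

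| r | m = 2% | m = 5% | m = 10% |
|---|---|---|---|
| 0.5 | −1.0% | −2.6% | −5.3% |
| 0.75 | −1.5% | −3.8% | −7.7% |
| 1.25 | −2.5% | −6.2% | −12.2% |
| 1.5 | −3.0% | −7.3% | −14.3% |

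For example, at m = 5% and r = 0.5: 0.025 / (0.95 + 0.025) = 2.6%. At r = 1.5: 0.075 / (0.95 + 0.075) = 7.3%.

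**Effect on the group mean.** If one of 25 similar participants has 20% of doses missing and the others none, the mean falls by 20% / 25 = 0.8%.

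**Per-infusion results.** With only known-dose infusions in numerator and denominator, IU/kg/infusion stays at 45 when r = 1. If recorded units were divided by the full infusion count, it would fall to 0.95 × 45 = 42.75 at m = 5%.

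**Substituting the mean recorded dose.** At r = 1 this gives 3123 / 0.95 = 3287 IU/kg/year, the actual figure.

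**The case against.** The strongest reply is that the denominator is inferred. No formula for annual consumption is printed, and the complete study period is defined under the ABR heading. A programmer who multiplied the mean recorded dose by infusions per year could claim to follow the rule and would largely avoid the bias. That stands as a limit on certainty. It is also a reason to print the formula, since two defensible programs would give different answers.

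Second, few doses may be missing. Protocol 8.1.1 requires for each home injection: "Individual vial number (bar code scan from vial label or manual entry) and units administered". The site verifies the diary data during regular contacts, and Protocol 6.4 adds: "Used and unused vials of study medication will be returned to the clinic at every site visit for accounting". The rule bites only on doses still missing after these checks. This limits the likely size but not the direction.

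Third, the endpoint is exploratory and the whole analysis is descriptive (Protocol 9.1, SAP 4.1). This also stands.

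Fourth, complete-case handling is reasonable for IU per infusion. Read plainly, the exclusion there removes the infusion from both numerator and denominator, so that result is consistent; only the denominator needs stating.

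A reader might go further and infer that the regimens will look more economical than they are. The documents do not support this. SAP 6.2 does not say that consumption is shown by regimen, there is no comparator, and Protocol 8.10 states that health economics is not evaluated.

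**Conclusion.** The point holds as a modest one. On the natural reading of SAP 4.5 and 6.2, total and annualised consumption are understated by the dose-weighted share of missing doses, and nothing visible in the SAP corrects or discloses this. At an assumed 5% missing, the shortfall is about 2.6% to 7.3% for dose ratios of 0.5 to 1.5.

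It is tempting to say that the shortfall simply equals the proportion of missing doses. That is true only if missing and recorded doses have the same mean, which need not hold where prophylaxis and bleed treatments are mixed.

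The conclusion rests on a full-period denominator, which the SAP implies but does not print, and on a missing rate that the documents do not give. Inhibitor results and ABR do not use the dose, and the exposure-day count keeps these infusions, so none of the three is affected.

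**What to change.** In SAP 4.5, Treatment administration:

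- Print the formula for annual consumption, with its time denominator.
- For totals and annualised consumption, recover a missing dose from vial records where available. Otherwise substitute the participant's mean recorded dose for the same infusion reason (prophylaxis or bleed treatment) and the same regimen period.
- For per-infusion summaries, keep the exclusion and state that only known-dose infusions enter numerator and denominator.
- Report the number of missing doses and the number imputed.

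The planned prophylaxis dose is a weaker substitute. Protocol 6.6 allows rounding up to full vials, and Protocol 6.1 has bleeds treated according to the product information, with possible modification of the dose on a scheduled day. The planned dose therefore need not match what was given.

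The cost is a short SAP text change and minor programming, plus the assumption that a participant's missing doses resemble his recorded ones. Only ABR is pooled for efficacy (SAP 6.2), so no pooled efficacy result changes. If comparability with the earlier studies is wanted (SAP 4.1), the figure under the present rule can be shown alongside.

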### 4.6 Blind Review/Validity review

The results of the final data assessment will be documented in the final list of important deviations, validity findings and assignment to analysis set(s). Any changes to the statistical analysis prompted by the results of the review of study data will be documented in an amendment and, if applicable, in a supplement to this SAP.

## 5. Analysis Sets

### 5.1 Assignment of analysis sets

Final decisions regarding the assignment of participants to analysis sets will be made during the review of study data and documented in the final list of important deviations, validity findings and assignment to analysis sets (see section 4.6).

#### Safety analysis set (SAF)

A participant will be included in the SAF if he received at least 1 infusion of study drug.

#### Intent to treat set (ITT)

A participant will be included in the ITT if he received at least 1 infusion of study drug and has any injection/bleeding data available.

#### Modified Intent-to-treat set (mITT)

A participant will be included in the mITT if he received at least 1 infusion of study drug and has injection/bleeding data for at least 3 months available.

A participant of study 13024 or study 15912 will only be included in the mITT if he entered the extension phase of the study.

## 6. Statistical Methodology

### 6.1 Population characteristics

All tables will be provided for the SAF and the mITT.

Demographics will include age, ethnicity, race, weight, height and BMI.

Baseline characteristics will include age at first treatment, type of first treatment regimen, type of FVIII gene mutation, family history of hemophilia, family history of inhibitor, presence of target joint, frequencies for specific target joints, previous FVIII treatment type, prior hemophilia treatment drug, medical history of concomitant diseases (e.g. HIV, hepatitis C, arthropathy, hypertension).

Summary statistics will be provided for number of bleeds and number of joint bleeds during the last 12 months prior to study and will be stratified by previous treatment type.

Descriptive statistics will be provided for the baseline activity level and previous dosing frequencies and dosages of study 19764.

#### Medical history, concomitant medication use

Medical history data as coded by MedDRA will be summarized by primary system organ class (SOC) and preferred term (PT). Prior and concomitant medications as coded by WHO-

DD will be summarized by ATC class and subclass. Medications taken before start of study drug will be considered prior medications, medications taken within the treatment period will be considered concomitant medications.

New concomitant medications that started after first treatment and belong to the ATC subclasses 'ANTIHEMORRHAGICS', 'BLOOD SUBSTITUTES AND PERfusion SOLUTIONS', and 'ANTIINFLAMMATORY AND ANTIRHEUMATIC PRODUCTS' will be presented by ATC subclass and standardized medication name. Factor VIII medications will be identified and grouped. A listing of new concomitant medications stratified by 'Antihemorrhagics', 'Blood substitutes and perfusion solutions', and 'Antiinflammatory and antirheumatic products' will be provided for study 19764.

### **Exposure and treatment duration**

Number of EDs and time in study will be analyzed by summary statistics. Number of EDs will be categorized into < 50 ED vs  $\geq 50$  - < 100 ED vs  $\geq 100$  ED. One ED is defined as a calendar day during which at least one infusion is taken by the participant.

### **Compliance**

Summary statistics for compliance (%) and time between prophylaxis injections (days) will be presented. Calculation of compliance is described in section [4.5](#).

Compliance will be categorized into < 95%,  $\geq 95\%$  -  $\leq 105\%$ ,  $> 105\%$ .

## **6.2 Efficacy**

The secondary objective of the study is to assess clinical efficacy. Unless otherwise mentioned, all efficacy analyses will be performed on the mITT population with a treatment period of at least 3 months. A comprehensive efficacy analysis will be done for study 19764. In addition, pooled results will be provided for the ABR.

The following descriptions refer to the analysis for the individual study data of 19764.

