### **8.3.7 Events of Special Interest**

Hypersensitivity reactions are a known and listed adverse drug reactions for FVIII products and have been reported with use of Jivi. Loss of efficacy of the drug product has also been reported in children < 6 years of age and may be associated with the development of antibodies to PEG. All such reported events occurred early in treatment, within the first 4 ED. Both of these events are defined in this study as adverse events of special interest and must be reported as adverse events.

In the event of such a hypersensitivity reaction or reported loss of efficacy of the treatment product, antibody and inhibitor testing will be obtained. Loss of efficacy needs to be documented by pre and post factor VIII levels around an injection of the Jivi, using appropriate laboratory measures, and be confirmed in the central laboratory.

CCI

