#### 9.4.1 Efficacy Analyses

The secondary objective of the study is to assess clinical efficacy. All efficacy analyses will be performed on the ITT population with a treatment period of at least 3 months.

The following efficacy variables will be analyzed:

- Annualized bleeding rate for joint and spontaneous bleeds
- Percentage of participants with 0 spontaneous bleeds within a 6-months treatment period
- Annualized number of total bleeds (sum of spontaneous bleeds and trauma bleeds)
- Incremental recovery will be summarized
- Total number of exposure per year will be documented in patient diaries and summarized
- Extent of exposure to study intervention during the study in terms of exposure days (ED) and injection characteristics (number of units, consumption dose/kg per participant/year, reason for treatment, type, location and severity of bleeds and response to treatment) will be summarized for each participant receiving any amount of drug.

Other pre-specified exploratory endpoints will be described in the statistical analysis plan finalized before database lock.

An integrated efficacy analysis will be done based on combined data from this study and studies 13024 Part A and 15912. Results will be provided by age groups.

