### **4.2 Handling of Dropouts**

A participant who discontinues study participation prematurely for any reason is defined as a dropout if the participant has already been administered at least one dose of study drug.

The reasons for withdrawal will be listed in a table. Dropouts will be included in all safety analyses. They will also be included in efficacy analyses if the treatment duration is  $\geq 3$  months. The ABR will be calculated for these participants. It is assumed that a shorter treatment duration will not be sufficient to correctly estimate the ABR and would bias the results. When calculating ABRs, the end of the measuring period for a dropout is defined as the later of last available infusion record from the electronic patient diary (ePD) or the last procedure in a scheduled visit, excluding the final visit.

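### SAP 6.2 applies a 3-month floor, justified only for the ABR, to per-bleed and per-infusion summaries, while Protocol 9.4.1 gives two conflicting populations for several of them

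*SAP*

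**What the plan says.** SAP 6.2 sets one default population: "Unless otherwise mentioned, all efficacy analyses will be performed on the mITT population with a treatment period of at least 3 months". Under SAP 5.1 a participant enters the mITT if he had at least one infusion and "has injection/bleeding data for at least 3 months available". The list under Other efficacy endpoints in SAP 6.2 includes "Bleeding attributes: type, location, intensity, number of infusions to control, response to treatment", as well as reason for infusion and IU/kg per infusion. It names no other population for these items. Its remark about complete study periods fixes the time window, not who is counted.

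The reason for the floor is in SAP 4.2: "It is assumed that a shorter treatment duration will not be sufficient to correctly estimate the ABR and would bias the results". No other reason is given.

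SAP 5.1 also defines an ITT set, which takes anyone who had an infusion and "has any injection/bleeding data available". No analysis in the readable text of the SAP is assigned to it.

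Protocol 9.4.1 makes two statements. It opens by placing all efficacy analyses on the ITT population with at least 3 months of treatment. Its bullet on extent of exposure and injection characteristics, which also covers units, consumption per kg per year and reason for treatment, then ends: "type, location and severity of bleeds and response to treatment) will be summarized for each participant receiving any amount of drug".

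**The concern.** A 3-month floor is reasonable for a rate, because one bleed in two weeks annualizes to an extreme value. That argument does not reach a rating of a single bleed, the number of infusions that bleed needed, or the dose of a single infusion. None of these is divided by follow-up time.

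The floor matters most if leaving early is related to how well the drug worked. The protocol treats loss of effect and hypersensitivity as events of special interest and says of those reported so far: "All such reported events occurred early in treatment, within the first 4 ED". Protocol 8.2.1 says that Jivi is to be stopped in such cases (part of that paragraph is blacked out), and Protocol 7.2 ends study participation when a participant discontinues. Such a participant has little follow-up, and the mITT rule would remove any bleed he treated with Jivi from the table meant to describe response.

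**Working it through.** The documents give no figure to reproduce here. The check has three parts.

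**1. Can an early loss-of-effect case reach the mITT?** Day of the 4th ED = 1 + 3 × dosing interval. The floor is 365.25 / 4 = 91.3 days.

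- Every 5 days (recommended start, Protocol 4.1): 1 + 3 × 5 = day 16.
- Twice weekly (interval 3.5 days): 1 + 3 × 3.5 = day 11.5.
- Every 7 days: 1 + 3 × 7 = day 22.

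A participant who stops within the first 4 ED is far short of day 91 on any regimen and cannot enter the mITT. One who continues past 3 months stays in.

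**2. How likely is at least one such case?** The documents give no rate for adults, so the rate p is an assumption. P(at least one) = 1 − (1 − p)^n, with n from the planned 25-30 participants (Protocol 1.1).

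| assumed p | n = 25 | n = 30 |
|---|---|---|
| 1% | 22% | 26% |
| 2% | 40% | 45% |
| 5% | 72% | 79% |

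**3. How far would the response table move?** Assume 25 participants followed for 1.5 years, so M = 25 × 1.5 × ABR bleeds, with none rated poor. Add one early leaver with k bleeds treated with Jivi, all rated poor. The poor share in the mITT is 0%; with everyone treated it is k / (M + k).

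| assumed ABR | M | k = 1 | k = 3 |
|---|---|---|---|
| 1 | 37.5 | 1/38.5 = 2.6% | 3/40.5 = 7.4% |
| 2 | 75 | 1/76 = 1.3% | 3/78 = 3.8% |
| 4 | 150 | 1/151 = 0.7% | 3/153 = 2.0% |

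The shift can also go the other way. If 5% of 37.5 bleeds are rated poor (1.875) and an early leaver adds 3 bleeds that all responded well, the poor share falls from 5% to 1.875 / 40.5 = 4.6%. With no early leavers, or none who treated a bleed with Jivi, nothing changes in the response table.

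**The case against.** The strongest reply is that the protocol sets the same floor. Protocol 9.3 builds 3 months of data into its ITT population and assigns that population to efficacy, and Protocol 9.4.1 repeats the rule. The SAP's mITT is in substance the protocol's ITT under another name. This stands. A reader might infer that the SAP breaks a clear protocol requirement, but the documents do not support that: the protocol contains two rules and the SAP followed the general one. What remains is that the any-amount-of-drug clause has effect only as an exception to the general rule. Protocol 9.2 also describes the ITT by available diary or injection data, with no floor.

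The clause has limits too. It does not name infusions to control a bleed or dose per infusion; for those, the argument rests only on the ABR-specific reason for the floor. It does include annualized consumption, which is better kept on the mITT.

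A reader might also infer that early failures disappear from the study. They do not. Loss of efficacy is an adverse event of special interest (Protocol 8.3.7), tabulated on the safety set (SAP 6.4). Antibody-positive participants are listed with their recovery results. SAP 6.1 shows exposure days and time in study for all treated participants. SAP 6.2 lists the number and kind of bleeds and time in study for those outside the mITT. Only the response rating and the infusions needed are not named there.

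Finally, the reported early immune responses were primarily in children under 6 (Protocol 2.3 and 8.2.1), whereas this study enrols adults. Cases may be few or none.

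**Conclusion.** The point holds as a mismatch between the stated reason for the floor and the tables it governs, together with an unresolved conflict inside Protocol 9.4.1. The practical gap is narrow: response ratings and infusions to control from anyone with under 3 months of data are left out of the summary tables, and the listing for excluded participants does not name them.

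The size is unknown and probably small. The 0.7-7.4% range rests on one early case, 1 to 3 poor-rated bleeds, an ABR of 1 to 4 and no other poor ratings, all assumed. A larger shift can be constructed: with 40 bleeds, 32 rated excellent or good, and two early leavers contributing 4 poor-rated bleeds, the favourable share is 32/40 = 80% for everyone treated against 32/36 = 89% in the mITT. That needs early failure in 2 of 25-30 participants (about 7-8%), each with two bleeds, and nothing in the documents supports that frequency in adults.

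It is also tempting to say that response is biased upward. The documents do not show this: participants may leave for any reason (Protocol 7.2), and the direction depends on how their bleeds responded. All analyses are descriptive and response is an exploratory endpoint (Protocol 8.1), so no formal conclusion is at risk. The change is still worth making: it is cheap, and it removes an exclusion that can depend on outcome.

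**What to change.** - In SAP 6.2, keep the mITT for the ABR and other annualized quantities. Present bleed attributes, response to treatment, infusions to control, reason for infusion and dose per infusion on the ITT set already defined in SAP 5.1.
- Reconcile the two statements in Protocol 9.4.1, saying which items follow the 3-month rule and which cover everyone treated, and where annualized consumption belongs. Align the ITT descriptions in Protocol 9.2 and 9.3 with the result.
- Add response to treatment and infusions to control to the listing of participants excluded from the mITT.

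The cost is SAP wording, a clarification of the protocol text, a population flag on a few descriptive tables and two listing columns. The downside is that a few tables will rest on a different population from the ABR, which needs a footnote, and that response figures may look slightly less favourable if early failures occur.
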